Continuous Glucose Monitoring in Hospitalized Patients With Diabetes Mellitus

NCT#04653454

12August2020

IRB Minimal Risk Protocol Template

Note: If this study establishes a human specimen repository (biobank) for research purposes, do not use this template. Use the Mayo Clinic Human Specimen Repository Protocol Template found on the IRB home page under Forms and Procedures at

[REDACTED]

First-time Use: Use this template to describe your study for a new IRB submission.

1. Complete the questions that apply to your study.
2. Save an electronic copy of this protocol for future revisions.
3. When completing your IRBe application, you will be asked to upload this document to the protocol section.

Modification: To modify this document after your study has been approved:

1. Open your study in IRBe. Click on the study 'Documents' tab and select the most recent version of the protocol. Save it to your files.
2. Open the saved document and activate "Track Changes".
3. Revise the protocol template to reflect the modification points, save the template to your files
4. Create an IRBe Modification for the study and upload the revised protocol template.

General Study Information

Principal Investigator: [name].

Study Title: CGM use in hospitalized patients with diabetes mellitus.

Protocol version number and date: Version 1.0, 8/12/2020

Research Question and Aims

Hypothesis: Patient's own CGM (continuous glucose monitor) used in the hospital will be as accurate as POC (point of care) glucose monitors and acknowledgement by providers of high and low glucose trends will prevent episodes of hyper and hypoglycemia.

Aims, purpose, or objectives:

1. To determine if patient's own CGMs worn in the non-ICU hospital setting have adequate accuracy for blood glucose monitoring when compared to point-of-care capillary glucose measurement.
2. To determine if alerts given by CGMs worn in the non-ICU hospital would prevent episodes of hyperglycemia and hypoglycemia.

Background (*Include relevant experience, gaps in current knowledge, preliminary data, etc.*):

Diabetes Mellitus (DM) affects approximately 34.2 million (10.5%) Americans. Hyperglycemia and hypoglycemia in hospitalized patients have been associated with unfavorable clinical outcomes, including higher rates of sepsis, deconditioning, mortality and longer hospital stay. Untreated

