All patients admitted to the hospital in inpatient or observation status and having a CGM monitor attached will be screened and identified by providers and nurses. An order will be placed by providers to continue patient's home CGM monitor use in the hospital. A CGM patient agreement describing the hospital policy for use of CGMs will be provided to the patient for signature. (see attached agreement) Patients will be encouraged to continue to wear their CGMs in the hospital unless their presence interferes with patients' medical care. CGM presence will be recorded by nursing in patient chart under LDA (lines, drains, airway) section. A daily report will be run and these patients identified. Patients will be approached by research staff and asked to be enrolled in the study. A research consent will be reviewed with the patients and will be provided to patients for signature. Patients will be asked to continue to use their home CGMs in the hospital. If the sensor will reach the end of life patients have the option to place a new sensor and follow manufacturer recommendations for calibration and setting. Patients are responsible to provide their own sensors, transmitters, readers during the hospitalization period. If it is determined that the current sensor will interfere with the in-hospital medical and surgical care (MRI testing, procedure at the site, etc.), patient will be asked by their providers to remove the sensor and transmitter. Patients will have the option to replace the sensor after the procedure if they so desire. Patients will continue to monitor their glucose via CGM and their approved devices. For flash sensors, patients will be asked to scan their sensor at least every 8 and as needed. CGMs that require calibration will be calibrated by patients using hospital POC glucose meter readings. .

Patients alerted by their CGM about low glucose levels or fast downward or upward trending will be asked to notify their nursing staff. A POC blood glucose check will be done by nursing staff to confirm the alert or the trend. Treatment decisions will be made based on POC readings.

During hospitalization patients will continue to have their blood glucose checked with POC glucose monitor per hospital policy.

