The study will use data that have been collected under another IRB protocol. Include in the Methods section and enter the IRB number from which the research material will be obtained. *When appropriate, note when subjects have provided consent for future use of their data and/or specimens as described in this protocol.*

Enter one IRB number per line, add more lines as needed

Data Specimens Data & Specimens _____

Data Specimens Data & Specimens _____

Data Specimens Data & Specimens _____

Data Analysis

Power analyses may not be appropriate if this is a feasibility or pilot study, but end-point analysis plans are always appropriate even if only exploratory. Provide all information requested below, or provide justification if not including all of the information.

Power Statement:

Data Analysis Plan:

Data will be described as percentages or means. Pearson χ^2 and Kruskal Wallis tests will be used to compare categorical and continuous variables respectively. Odds ratios, 95% confidence intervals and p-values will be reported for each model. All tests of significance will be 2-sided and the level of statistical significance will be set at p-value < 0.05.

Mean Absolute Relative Differences will be calculated between matched pairs of POC monitors and the closest CGM reading (within 5 minutes of POC). Additionally, level of agreement between the two devices will be examined with Bland-Altman plots, with particular attention focused on detection agreement in range (70-180 g/dl). Poisson or negative binomial regression will be utilized to assess count variables such as number of alarms, nurse notification, and hypo or hyperglycemia events adjusting for patient characteristics. Finally, longitudinal analysis will be conducted to determine differences associated with medications, clinical parameters or diagnosis. Analysis will seek to define if there are any differences between CGM and POC measurement based on these changes.

Endpoints

Primary: CGM accuracy - mean absolute relative difference (MARD)

Secondary:

- CGM accuracy at detection of hypo or hyperglycemia episodes when compared with POC monitors. (MARD for readings <70g/dl, >180g/dl, >250g/dl)
- CGM accuracy for detecting time in range (70-180 g/dl MARD).
- Number of CGM alarms and the clinical result of these alarms: nurse notification, treatment of hypo or hyperglycemia episodes, treatment for rapid declining glucose alarms.

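### The alarm-result endpoint covers all CGM alarms, but patients are asked to report only low and fast-trend alerts; split the result by alarm type and analyse notifications per requested alarm

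*Combined protocol and SAP*

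**What the plan says.** Under Study Design and Methods, the instruction to patients is: "Patients alerted by their CGM about low glucose levels or fast downward or upward trending will be asked to notify their nursing staff". The next step applies to those reports: "A POC blood glucose check will be done by nursing staff to confirm the alert or the trend". No other text in the file asks patients to report a high-glucose alert. Routine testing runs in parallel: "During hospitalization patients will continue to have their blood glucose checked with POC glucose monitor per hospital policy". The same section mentions a further document that is not in the file: "A CGM patient agreement describing the hospital policy for use of CGMs will be provided to the patient for signature".

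The secondary endpoint, listed under Outcomes measured and again under Endpoints, is wider: "Number of CGM alarms and the clinical result of these alarms: nurse notification, treatment of hypo or hyperglycemia episodes". It goes on to name treatment after alarms for a rapid decline. The Data Analysis Plan states: "Poisson or negative binomial regression will be utilized to assess count variables such as number of alarms, nurse notification, and hypo or hyperglycemia events", with adjustment for patient characteristics. It gives no split by alarm type and no denominator or offset.

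Under Research Question and Aims, Aim 2 reads: "To determine if alerts given by CGMs worn in the non-ICU hospital would prevent episodes of hyperglycemia and hypoglycemia". The hypothesis is worded in terms of trends: "acknowledgement by providers of high and low glucose trends will prevent episodes of hyper and hypoglycemia".

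**The concern.** The endpoint takes in more alarms than the instruction that produces notifications. Call a high-level alert without a fast rise a steady-high alert. It counts as a CGM alarm, and hyperglycemia treatment is one of the listed results, but nobody is asked to report it and no confirming check is requested for it.

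An unreported steady-high alert therefore has two possible meanings: the patient did not act, or the patient was never asked. A pooled notification result cannot separate them. In the planned count regression, a patient group with more steady-high alerts among its alarms could show fewer notifications for that reason alone, and the model could credit the difference to a patient characteristic. What is at stake is the reading of one secondary endpoint.

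**Working it through.** The plan gives no figure to reproduce. It states no alarm mix and no reporting rate, so the check is a comparison of texts followed by an example on assumed values.

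**Comparison.** The grouping into four alarm types is made here; the documents list no such types.

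| Alarm type | Notification and check requested | Within the alarm-result endpoint |
|---|---|---|
| Low glucose | yes | yes |
| Fast fall | yes | yes |
| Fast rise | yes | yes |
| Steady-high | no | yes |

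**Inputs (all assumed).** Two patients with N = 10 alarms each; reporting rate for requested alerts r = 0.8; steady-high share h = 0.2 for patient A and 0.6 for patient B; unasked reporting rate for steady-high alerts v, varied from 0 to 0.8.

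**Pooled count.** Expected notifications = N × [(1 − h) × r + h × v]. For A this is 10 × (0.8 × 0.8 + 0.2v) = 6.4 + 2v. For B it is 10 × (0.4 × 0.8 + 0.6v) = 3.2 + 6v.

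| v | A | B | Ratio B/A |
|---|---|---|---|
| 0 | 6.4 | 3.2 | 0.50 |
| 0.2 | 6.8 | 4.4 | 0.65 |
| 0.4 | 7.2 | 5.6 | 0.78 |
| 0.6 | 7.6 | 6.8 | 0.89 |
| 0.8 | 8.0 | 8.0 | 1.00 |

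The two patients respond identically to what they were asked to do, yet the ratio runs from 0.50 to 1.00. It is also 1.00 whenever h is the same for both.

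**Which analysis removes the artefact.**

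- Requested types only, as a count: A has 8 × 0.8 = 6.4 and B has 4 × 0.8 = 3.2, a ratio of 0.50 at every v. Restriction alone does not help, and at v = 0.8 it moves the ratio from 1.00 to 0.50.
- All types, per alarm: at v = 0, 6.4/10 = 0.64 against 3.2/10 = 0.32, again a ratio of 0.50. A denominator of all alarms does not help either.
- Requested types only, per requested alarm: 6.4/8 = 0.80 against 3.2/4 = 0.80, a ratio of 1.00 at every v.

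Both the restriction and the matching denominator are needed.

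**The case against.** The strongest case on the other side is that the instruction is a sensible choice. Asking for lows and trends, and leaving other highs to routine POC testing, limits nurse calls and finger-sticks. Upward trends, the alerts most likely to come before hyperglycemia, are requested, which fits the hypothesis. If the word fast qualifies only downward trends, slow rises are requested too and only plateaus are left out. The patient agreement may ask for more. The endpoint already names one result specific to an alarm type, so some reporting by type may be intended. The size rests entirely on assumed values.

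All of this stands, and it narrows the point. It does not remove it: on either reading of the sentence, some high alerts fall inside the endpoint and outside the request, and the count model is not said to separate them.

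A reader might infer more, without support from the documents:

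- *Patients may not report high alerts.* The text does not ask for such reports; it does not forbid them.
- *The hyperglycemia part of Aim 2 is left out.* Upward trends are covered. A steady-high alert sounds once glucose is already above the alert level. No comparison group is described, so prevention cannot be shown for any alert type, requested or not.
- *The accuracy results are compromised.* MARD and time in range do not depend on which alerts are reported in the way that the notification result does.

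**Conclusion.** The mismatch is real but minor. Unless the patient agreement says otherwise, a low notification figure for high alerts would partly reflect the instruction, and a pooled notification count would mix the reporting rule with behaviour. Hyperglycemia treatment after an unreported high alert cannot be credited to the alert, because routine POC checks continue regardless.

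The size is unknown. The example gives ratios from 0.50 to 1.00 under assumed alarm mixes and reporting rates. There is no effect if the mix is the same across patient groups, or if high alerts are reported as often as requested ones. It would be too strong to conclude that the plan must ask patients to report high alerts; that is a choice for the ward and the investigator.

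**What to change.** 1. Tabulate alarms, notifications and treatments by alarm type: low, high, fast fall, fast rise. Take the type from the CGM device data or, if it is not recorded, derive it from the glucose trace by a rule written in advance. Count an alert that is both high and fast-rising as requested.
2. Base the notification result on the requested types only, analysed per alarm: Poisson or negative binomial regression with the log number of requested-type alarms as offset.
3. Give high-level alerts, with any notifications and treatments that followed, descriptively.
4. Check the patient agreement. If it already asks for high alerts, bring the Methods sentence into line with it and treat them as a requested type.

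The cost is one sentence in the endpoint, one in the analysis plan and one split table; accrual, procedures and the primary endpoint do not change. The downsides are that the study draws no notification conclusion for high-level alerts, that the split needs alarm type to be identifiable (the documents do not say whether it is), and that a patient with no requested-type alarm does not enter the offset model, so the number of such patients should be reported.

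Adding high alerts to the notify sentence is optional. For example, reports could be requested above 250, a cut-off already used in the Endpoints section. That would mean more nurse calls and finger-sticks and more high-range pairs in the MARD data, and alerts set at or below 250 would still not be requested.

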hypoglycemia may lead to neurological damage, cognitive decline, seizures and coma. Additionally, the management of the diabetic complications doubles the inpatient cost per capita compared to non-diabetic patients.

Current standard of care in the hospital recommended by the national guidelines is the bedside point-of-care (POC) glucose capillary testing performed before meals and at bedtime. This approach however does not provide continuous 24-h glucose measurement and fails to detect nocturnal or asymptomatic hypoglycemia or hyperglycemia, all of which are common insulin therapy complications.

Continuous Glucose Monitoring (CGM) represents an alternative with the potential to assist making personalized therapy decisions. It measures levels of interstitial glucose every 5-15 min, which provides better assessment of nocturnal or asymptomatic hypoglycemia or hyperglycemia and shows glycemic patterns following treatment interventions. The ability to monitor glucose more frequently will also allow for timely interventions, and thus hyperglycemia and hypoglycemia episodes can be reduced. There have been studies demonstrating improved glycemic control in insulin-treated DM patients using CGM in outpatient setting, and even a few studies describing the use of CGM in non-ICU hospitalized patients.

Prospective studies evaluating the use of the newer CGMs in non-critically ill hospitalized patients are lacking. The aim of our study therefore was to compare the accuracy of patient's own CGM monitor worn in the hospital in detecting blood glucose levels by comparing them with those measured by a POC blood glucose capillary test.

Study Design and Methods

Methods: *Describe in lay terms, completely detailing the research activities that will be conducted by Mayo Clinic staff under this protocol.*

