Treatment of the DM and associated complications, dosing of the insulin, change from PO to insulin treatment and back to PO medications during hospitalization or at discharge will be guided by the admitting team with as needed help from the inpatient Endocrinology Consultation Service.

Decisions about insulin dosing or other medication use designed to treat hyper or hypoglycemia episodes or underlying diabetes mellitus will be made based on hospital POC blood glucose meters and not based on CGM readings alone.

Patients will be asked to give the research team “provider access” to their cloud CGM software, or to allow the team to download their CGM data prior to discharge if their reading devices do not automatically synchronize with the cloud software.

CGM data will be compared with POC blood glucose monitoring obtained in the hospital. Different patient variables (demographics, comorbidities, labs and vitals, administered medications) will be collected from electronic health record and will be evaluated to determine if they would interfere with CGM readings. The accuracy of CGM for glucose measurement in the hospital will be calculated.

Outcomes measured:

CGM accuracy when compared with POC monitors.

CGM accuracy at detection of hypo or hyperglycemia episodes when compared with POC monitors.

Number of CGM alarms and the clinical result of these alarms: nurse notification, treatment of hypo or hyperglycemia episodes, treatment for rapid declining glucose alarms.

Materials:

CGMs (sensors, transmitters and readers) belong to patients

Provider access to cloud CGM program will be granted to the research team by the patient.

Personnel:

A research assistant that will identify the patients and enroll them into the study.

Subject Information

Target accrual is the proposed total number of subjects to be included in this study at Mayo Clinic. A “Subject” may include medical records, images, or specimens generated at Mayo Clinic and/or received from external sources.

Target accrual: 150

Subject population (children, adults, groups): Admitted adult medical and surgical patients with Diabetes Mellitus type I or II that have their own CGM monitor present on admission or able to be placed after admission.

Inclusion Criteria:

Patients with Type 1 or 2 Diabetes Mellitus,

Patients 18 years of age or older,

Patients admitted under medical or surgical services.

Patients treated with diet alone, insulin (SQ, insulin pump) or oral hypoglycemic medications.

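### Patient-owned CGMs of different types share one overall MARD, and no analysis includes device type, so a less accurate device can be hidden and the search for interfering factors is open to confounding by device

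*Combined protocol and SAP*

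**What the plan says.** Under Study Design and Methods, the Materials paragraph says "CGMs (sensors, transmitters and readers) belong to patients". No make or model is required or excluded.

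The Methods make provision for more than one kind of device:

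- On scanning: "For flash sensors, patients will be asked to scan their sensor at least every 8 and as needed"
- On replacement: "If the sensor will reach the end of life patients have the option to place a new sensor"
- On calibration: "CGMs that require calibration will be calibrated by patients using hospital POC glucose meter readings"

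The Background says of CGM in general: "It measures levels of interstitial glucose every 5-15 min".

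Endpoints names one primary measure, the MARD of CGM. The secondary MARDs are split by glucose range only. The Data Analysis Plan pairs each POC value with the nearest CGM reading no more than 5 minutes away, and its Bland-Altman analysis treats CGM and POC as two devices.

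For the interference question, the Methods say "Different patient variables (demographics, comorbidities, labs and vitals, administered medications) will be collected from electronic health record". The count models adjust for patient characteristics. The longitudinal analysis looks at drugs, clinical measures and diagnoses. Device type is not a stratum, subgroup or model term in any of these.

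**The concern.** Two things are at stake.

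The first is how the primary result is read. An average over device types can look acceptable while one type performs worse. It also changes with the local share of each type, even when no device changes. A hospital with a different mix could not carry the figure over.

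The second is the secondary endpoint on factors that interfere with CGM readings. The study enrols type 1 and type 2 diabetes, treated by diet, oral agents, injected insulin or pump. It is plausible, though the documents do not show it, that device type differs between these groups. If device accuracy also differs, a diagnosis or long-term drug more common among users of one device could be reported as interfering when the device accounts for the difference.

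The plan itself contains two routes by which results could differ by device. Some devices are calibrated to the comparator, which can pull their readings towards it. The matching window may also keep a smaller share of POC tests for a device that records less often.

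**Working it through.** The documents give an accrual target of 150 but no SD, margin, device-specific MARD or device mix, so there is no derived figure to reproduce. The check is a reading of the text followed by illustrations. Every MARD, SD, mix and prevalence below is an assumption.

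**1. Is there a device term?** The primary and secondary endpoints, the Bland-Altman analysis, the count models and the longitudinal analysis were each read for one. None has it. The plan does not use the word pooled; that follows from one MARD with no device stratum.

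**2. Dependence on mix.** Overall MARD = w × MARD_A + (1 − w) × MARD_B, where w is the share of matched pairs from device A.

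| MARD A, B (assumed) | w = 0.8 | w = 0.2 | Shift |
|---|---|---|---|
| 9%, 11% | 9.4% | 10.6% | 1.2 points |
| 9%, 14% | 10.0% | 13.0% | 3.0 points |
| 9%, 17% | 10.6% | 15.4% | 4.8 points |

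For example, 0.8 × 9 + 0.2 × 14 = 10.0 and 0.2 × 9 + 0.8 × 14 = 13.0. For scale, with one value per patient the 95% CI half-width at N = 150 is 1.96 × SD / √150. This gives 0.64, 0.96 and 1.28 points for assumed between-patient SDs of 4, 6 and 8.

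**3. Matching window.** Reading the window as 5 minutes either side, the chance that a POC test finds a match is min(1, 10 / recording interval). It is 100% at 5 minutes and 10/15 = 67% at 15 minutes. With equal POC tests per patient, a 50/50 mix of patients becomes 0.5 / (0.5 + 0.5 × 0.667) = 60% of pairs from the 5-minute device. With MARDs of 9% and 14%, the overall value moves from 11.5% to 0.6 × 9 + 0.4 × 14 = 11.0%.

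**4. False difference for a factor with no effect.** False difference = device gap × (share of the worse device among exposed − share among unexposed). With devices split 50/50 and factor prevalence of 30% on one device and 70% on the other, the shares are 0.7 and 0.3, a difference of 0.4. With 40% and 60% the difference is 0.2. With equal prevalence it is 0.

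**5. False-positive rate.** Simulation: 150 patients, devices 50/50, one MARD per patient, SD 6, a factor with no effect, a linear model tested two-sided at 0.05, and 4000 runs per row.

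| Gap (points) | Prevalence by device | False difference | Rate without device term | Rate with device term |
|---|---|---|---|---|
| 2 | 50/50 | 0 | 5.5% | 5.7% |
| 2 | 40/60 | 0.4 | 7.4% | 4.8% |
| 2 | 30/70 | 0.8 | 13.5% | 5.1% |
| 5 | 50/50 | 0 | 4.3% | 4.4% |
| 5 | 40/60 | 1.0 | 16.0% | 5.0% |
| 5 | 30/70 | 2.0 | 46.4% | 5.2% |
| 8 | 50/50 | 0 | 5.1% | 4.8% |
| 8 | 40/60 | 1.6 | 29.0% | 4.9% |
| 8 | 30/70 | 3.2 | 78.2% | 5.0% |

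This is a purely between-patient comparison. It therefore represents factors fixed within a patient, not drugs started or stopped during the stay.

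**The case against.** The strongest reply is that the primary endpoint answers the question asked. Aim 1 concerns patients' own CGMs, and an average over the devices that patients bring is a legitimate answer. This stands. A reader might infer that the primary MARD is invalid; the documents do not support that. Dependence on the mix limits how far the figure carries over. The plan also sets no MARD threshold for adequacy, so nothing shows that any device would fail.

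A reader might also infer that device model will go unrecorded. That is not supported either. The list of variables covers patient data from the health record. Device data arrive separately, through access to the CGM software or a download before discharge. What is missing is their use in the analysis.

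Nor can one say that the interference search is confounded. That needs both an accuracy gap between devices and an association between device and factor, and the documents give neither. The longitudinal analysis may also be meant as a within-patient comparison. If so, it would remove much of the device effect for factors that change during the stay, provided that patients keep one device type. But no such model is specified, and it would not help with diagnosis, comorbidity or long-term medication.

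The heterogeneity is also conditional. The flash and calibration provisions cover devices that may appear, and the 5 to 15 minute interval is general background. The enrolled mix is unknown.

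Finally, analysts might add device without being told to. Nothing in the plan says so, and a split chosen after the data are seen carries less weight than one set in advance.

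**Conclusion.** The point holds in a limited form. The plan allows for a mix of devices, some calibrated to the comparator, and includes device type in no analysis. The overall MARD remains a valid description of the enrolled mix, but it can hide a worse device. The interference search is open to confounding by device, mainly for factors fixed within a patient and less for factors that change during the stay if within-patient contrasts are used.

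The size cannot be known from the documents. Under the assumed gaps of 2 to 8 points and unequal prevalences of 40/60 to 30/70, the false difference is 0.4 to 3.2 points; with equal prevalence it is 0. At SD 6, the matching false-positive rates run from about 7% to 78% without a device term and stay near 5% with one. Treatment decisions rest on POC readings, so the consequence is for interpretation of the results. This is a cheap improvement, not a flaw in the primary endpoint.

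**What to change.** - Keep the overall MARD as the primary endpoint, and state that it describes the enrolled device mix.
- Take device model and POC-calibration status from the CGM download.
- Beside the overall MARD, report MARD and the number of matched pairs by device type, with 95% CIs clustered by patient. The pair counts will show whether the matching window keeps fewer pairs for some devices.
- Include device type, with POC-calibration status, as a fixed effect in the longitudinal models of drugs, clinical measures and diagnoses.

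The cost is small: two fields drawn from data that the team already plans to obtain, one added table, and the device term in the models. The downside is wide intervals for uncommon devices, which may need to be grouped. The grouping rule should be set before the comparison with POC is run.

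### The only model named for the clinical result of CGM alarms is count regression with no alarm denominator, so as written it mixes how often alarms occur with how often they are acted on

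*Combined protocol and SAP*

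**What the plan says.** The secondary endpoint, listed under Endpoints and again among the measured outcomes in Study Design and Methods, is "Number of CGM alarms and the clinical result of these alarms: nurse notification, treatment of hypo or hyperglycemia episodes, treatment for rapid declining glucose alarms".

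Methods describes a sequence for each alert. "Patients alerted by their CGM about low glucose levels or fast downward or upward trending will be asked to notify their nursing staff". Then "A POC blood glucose check will be done by nursing staff to confirm the alert or the trend". Treatment decisions rest on the POC reading.

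The Data Analysis Plan names one model for these quantities: "Poisson or negative binomial regression will be utilized to assess count variables such as number of alarms, nurse notification, and hypo or hyperglycemia events". The only adjustment named is for patient characteristics. The plan states no offset, alarm denominator, time window or rule linking an alarm to what followed. Treatment after an alarm is assigned to no method, although the list of count variables is open-ended.

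The remaining text is general. "Data will be described as percentages or means", chi-square tests are planned for categorical variables, and odds ratios are to be reported for each model. None of this is tied to alarms.

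Aim 2 (Research Question and Aims) reads: "To determine if alerts given by CGMs worn in the non-ICU hospital would prevent episodes of hyperglycemia and hypoglycemia".

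**The concern.** The clinical result of an alarm is conditional on the alarm: given that it sounded, was the nurse told, and was treatment given? A notification count regressed on patient characteristics answers another question, namely which patients accumulate more notifications. Because notifications follow alarms, a characteristic that raises alarm frequency raises the notification count even if each alarm is acted on less often.

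Unequal alarm exposure is plausible here. The study enrols type 1 and type 2 diabetes, and patients on diet alone, oral agents, injected insulin and pumps. It includes flash sensors that the patient scans, and it allows sensors to be removed and replaced. If the stated models are run as written, the report could describe alarm burden as though it were alarm response, and the share of alarms leading to notification or treatment need not appear at all.

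There is also a data issue. The record items listed for collection are demographics, comorbidities, labs and vitals, and administered medications. No source or time stamp for nurse notification is described, so the link may be hard to recover later.

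**Working it through.** **Inputs.** From the documents: the endpoint, the count models and their adjustment as above, target accrual 150, and two-sided testing at 0.05. They give no alarm rate, response rate or power calculation, so there is no stated figure to reproduce. All rates below are assumptions.

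**Step 1: identity.** Mean notifications per patient = mean alarms per patient × share of alarms notified. For groups A and B:

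count ratio = (alarm-rate ratio) × (per-alarm response ratio).

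If A responds less per alarm (response ratio below 1), the count ratio still exceeds 1 whenever the alarm-rate ratio is greater than 1 / (response ratio).

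**Step 2: illustration, equal stay and wear.** A has 12 alarms with 40% notified; B has 4 with 70% notified.
- Notifications per patient: 12 × 0.4 = 4.8 and 4 × 0.7 = 2.8.
- Count ratio: 4.8 / 2.8 = 1.71.
- Per-alarm response ratio: 0.4 / 0.7 = 0.57.
- Reversal threshold: 0.7 / 0.4 = 1.75. The alarm-rate ratio is 12 / 4 = 3.0, so the direction reverses.

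The like-for-like comparison is 1.71 with 0.57. The per-alarm odds ratio, (0.4/0.6) / (0.7/0.3) = 0.29, is on another scale and would exaggerate the contrast.

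**Step 3: sensor time as exposure.** Dividing by monitored time turns alarms per patient into alarms per day. The alarm rate still multiplies the response share, so this offset alone does not separate them.

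**Step 4: when it reverses.**

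| A: alarms, share | B: alarms, share | Alarm-rate ratio | Reverses above | Count ratio | Per-alarm ratio |
|---|---|---|---|---|---|
| 10, 30% | 4, 60% | 2.50 | 2.00 | 1.25 | 0.50 |
| 8, 40% | 4, 60% | 2.00 | 1.50 | 1.33 | 0.67 |
| 12, 50% | 4, 80% | 3.00 | 1.60 | 1.88 | 0.625 |
| 5, 50% | 4, 60% | 1.25 | 1.20 | 1.04 | 0.83 |
| 4.5, 50% | 4, 60% | 1.125 | 1.20 | 0.94 | 0.83 |
| 4, 50% | 4, 60% | 1.00 | 1.20 | 0.83 | 0.83 |

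With similar alarm rates there is dilution but no reversal. With equal rates the two ratios agree.

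**Step 5: behaviour at 150 patients.** Simulation with two groups of 75 and 500 runs per case. Assumed: gamma-Poisson alarms with dispersion 1, and beta-binomial response with within-patient correlation 0.1. A negative binomial model of notifications was compared with a per-alarm analysis, using patient-level robust standard errors. The per-alarm analysis was fitted both as a binomial model and as a Poisson model with log(alarms) offset; the two gave the same percentages.

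| Case (A vs B) | Count model above 1 | Count model significantly above 1 | Per-alarm analysis significantly below 1 |
|---|---|---|---|
| 10 at 30% vs 4 at 60% | 83% | 20% | 100% |
| 8 at 40% vs 4 at 60% | 93% | 31% | 97% |
| 12 at 50% vs 4 at 80% | 100% | 91% | 100% |
| 5 at 50% vs 4 at 60% | 57% | 5% | 45% |
| 4 at 40% vs 4 at 60% | 3% | 0% | 97% |

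In every case the true per-alarm response is lower in A.

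**The case against.** The strongest reply is that the plan is brief rather than wrong. Its list of count variables is open-ended, and it never says that the counts are analysed separately or per patient; that is the natural reading, not stated text. A log(alarms) offset fits inside the named Poisson and negative binomial models. A percentage of alarms notified fits the general descriptive line. The mention of odds ratios, which are not what count models yield, leaves room for a binary-outcome model.

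This stands to a point. A reader might infer that the plan is incapable of showing the result of alarms. The documents do not support that: a linked analysis is unspecified, not excluded. But the general lines are not assigned to alarms, and the one method that is assigned answers a different question if followed as written.

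A reader might also infer that the count model will reverse the comparison. That too is unsupported: reversal needs a large enough difference in alarm rates, and no rates are given. Even in the reversing cases above, a significantly wrong result was sometimes uncommon (20% and 31% in two of them).

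It is also fair that no aim asks which patients respond to alarms. The planned adjustment for patient characteristics nevertheless produces between-patient contrasts, and those are the ones affected.

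**Conclusion.** The point holds in a limited form. The one model named for this secondary endpoint has no alarm denominator and no link between alarm, notification and treatment, so as written it does not estimate the clinical result of alarms. Its error for a given characteristic is a factor equal to the alarm-rate ratio: none when alarm rates are equal, threefold in the illustration of 1.71 against 0.57. Direction reverses only above the threshold in the working. Those sizes rest on assumed rates, and the simulated percentages also on the assumed dispersion and within-patient correlation.

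The plan should be changed on this point, but the primary MARD analysis is untouched. A reader might infer that an alarm-level analysis would settle Aim 2. It would not: it describes the alarm-response chain, and without a comparator it does not by itself show that alerts prevent episodes.

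**What to change.** - **Alarm frequency:** keep the Poisson or negative binomial model, with monitored time as offset.
- **Unit for notification and treatment:** the alarm, or an alarm episode with repeat alarms grouped by a stated rule. Link each to the notification, POC and medication records within a prespecified time window.
- **Denominators:** define them by alarm type. For notification, count only the alerts for which Methods asks patients to tell nursing (low glucose, or fast downward or upward trend). A plain high-glucose alert is not named there, so counting it would register failures that nobody was asked to prevent.
- **Treatment:** report it according to whether the POC check confirmed the alert, because treatment follows the POC reading. Otherwise an unconfirmed alert left untreated looks like a missed treatment.
- **Reporting and model:** give the share at each step. Model it with a patient-clustered binomial model (GEE or random intercept), or with a count model using a log(alarms) offset.

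The cost is analysis wording, some linkage work, and a brief chart entry of the notification at the POC check that nurses already perform. The chart entry needs to be in place while data are being collected; the rest can be settled in the analysis plan.
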